Note: Individuals with a well-established DSM-IV diagnosis of autistic disorder, Asperger's disorder, or pervasive developmental disorder not otherwise specified should be given the diagnosis of autism spectrum disorder. Individuals who have marked deficits in social communication, but whose symptoms do not otherwise meet criteria for autism spectrum disorder, should be evaluated for social (pragmatic) communication disorder.

Specify if:

- With or without accompanying intellectual impairment
- With or without accompanying language impairment
- Associated with a known medical or genetic condition or environmental factor
- Associated with another neurodevelopmental, mental, or behavioral disorder
- With catatonia

Project Goals

The goal of the proposed study is to evaluate the safety and feasibility of oral Glutathione in children and adolescents who have Autism Spectrum Disorder. Twenty-four subjects with ASD will receive 12 weeks of oral Glutathione reduced. The hypothesis to be tested is that: Oral Glutathione will be effective in increasing the blood level of Glutathione, which may help to decrease some problem behaviors and irritability in this particular ASD population. The second aim of this study is to evaluate the tolerability of oral Glutathione. The proposed study may provide needed data for future studies aimed at the treatment of aggressive behaviors that can be seen in this patient population.

Background and Significance

Autism Spectrum Disorder is a complex neurodevelopmental disorder, which can involve impaired social interaction, impaired language and communication, limited interest, repetitive/ritualistic behaviors and sometimes aggressive behavior (3). Although Autism Spectrum Disorder has been described in medical literature for years, it remains poorly understood and the exact etiology and neurobiology are not quite clear. However, an emerging topic in research is the imbalance between bodily oxidative systems and anti-oxidative stress in Autism Spectrum cases (i.e. redox systems). Glutathione is involved in neuro-protection against oxidative stress and play a major role in our anti-oxidative stress systems, which may mean that decreasing oxidative stress over time could be a possible treatment for some problem behaviors that are seen in Autism Spectrum Disorder (3).

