N-acetylcysteine is an antioxidant agent and glutamatergic modulator, it is also a precursor to Glutathione via cysteine production. Glutathione is found naturally in the human body and produced by the liver; it is a 3-amino acid (tripeptide) that is composed of cysteine linked to glutamate and followed by glycine attachment (Figure 1). When N-acetylcysteine is de-acetylated, cysteine is provided to feed into the transsulfuration pathway, leading to the production of Glutathione (9). Glutathione is also found in plants, all mammalian tissue, fungi and some bacteria; and it is considered a key determinant of redox signaling, vital in detoxification of xenobiotics, regulates cell proliferation, apoptosis and immune function (6, 7). As mentioned, there is some evidence that antioxidant agents may be beneficial in reducing irritability or aggression in children with ASD. Therefore, we believe that by testing the feasibility of using oral Glutathione directly, and examining the anticipated changes in Glutathione blood level, as we are bypassing the transsulfuration pathway and providing Glutathione supplementation to the body, may be beneficial for ASD patients. Given that Glutathione may have various advantages over other pharmacological agents in treating children with ASD, and it is an all-natural supplement, it can be a promising treatment for irritability and problem behaviors seen in this population and may play a role in correcting the lower levels of plasma reduced Glutathione often observed in children with ASD.

Figure 1: Image NAC de-acetylation and formation of Glutathione (9)

Aims

- 1) To determine whether Glutathione given over a 12-week period increases plasma Glutathione level in a sample of 24 children aged 4-17 years old with a history of Autism Spectrum Disorder.
- 2) To determine the feasibility of using oral Glutathione in this patient population
- 3) To test whether oral administration of Glutathione supplement is well tolerated as a medical food in children with ASD.

Overall, we will examine the effects of Glutathione in children with Autism Spectrum Disorder. Evidence suggests that Glutathione may reduce reactive oxygen species that can accumulate in patients with ASD and thereby may help to decrease significant problem behaviors seen in this population. We hypothesize that oral Glutathione will be safe and well tolerated in patients with Autism Spectrum Disorder.

METHODS

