The study will consist of **12 weeks of open label trial** with treatment of oral Glutathione in 24 subjects with ASD; the subjects will be recruited at the University of Chicago. Subjects will be seen every two weeks for the first month and then every four weeks for the remaining two months with one final visit at the end of the study for a total of 5 visits.

Study Location

This is a single-site trial in the United States, with a total of 24 subjects aged 4-17. The Principal

Page 6 of 17 IRB19-0017 Version 2; date: 4/11/19 Investigator for this study is:

[name]. Professor of Child and Adolescent Psychiatry University of Chicago [name]

All subjects will be seen in the Department of Child and Adolescent Psychiatry at the University of Chicago Medical Center at [name]. The offices are connected to the Department of Psychiatry and provide confidential interview rooms and facilities.

Investigational Agent

Glutathione (GSH) Reduced (Oral Capsules - Jarrow Brand)

- for patients 40kg or less: 500 mg by mouth twice a day for two weeks, then 1000 mg by mouth twice a day for ten weeks.
- for patients greater than 40 kg: 500 mg by mouth twice a day for two weeks, then 1000 mg by mouth twice a day for two weeks, then 1000 mg by mouth each morning and 2000 mg by mouth every afternoon for eight weeks.
- Dosages will be increased based on tolerability and the monitoring of any potential GI side effects as determined by the investigator.

Dosing Regimen for ≤40kg group (BID dosing throughout study)

Week 0 (Visit 1) – Week 2 (Visit 2): 1000mg/day (500mg po qam and 500mg po qpm)
Week 2 (V2) – Week 12 (V5): 2000mg/day (1000mg po qam and 1000mg po qpm)

Dosing Regimen for ≥40kg group (BID dosing throughout study)

 Week 0 (Visit 1) – Week 2 (Visit 2):
 1000mg/day (500mg po qam and 500mg po qpm)

 Week 2 (V2) – Week 4 (V3):
 2000mg/day (1000mg po qam and 1000mg po qpm)

 Week 4 (V3) – Week 12 (V5):
 3000mg/day (1000mg po qam and 2000mg po qpm)

Maximum Amount of Study Drug Needed

V1: 1000mg = 2 (500mg) pills x 14 days = 28 pills V2: 2000mg = 4 (500mg) pills x 14 days = 56 pills V3: 3000mg = 6 (500mg) pills x 28 days = 168 pills V4: 3000mg = 6 (500mg) pills x 28 days = 168 pills

V5: none dispensed (end of study) total per subject: 420 pills

TOTAL PILLS for 24 subjects = \sim 10,080pills maximum (based on recruiting patients \geq 40kg)

SUMMARY OF DATA COLLECTION AND STUDY PROCEDURES BY VISIT							

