		Visit					

Page 7 of 17 IRB19-0017 Version 2; date: 4/11/19

	Screening	1	2	3	4	5	6			
Consent Forms:	Х									
Medical Procedures on Child										
Blood draw		Х					Х			
Heart rate		х	Х	Х	Х	Х	Х			
Blood pressure		х	Х	Х	Х	Х	Х			
		Pare	nt Reports	on Child						
Aberrant Child Checklist	Х	Х	Х	Х	Х	Х	Х			
Social responsiveness Scale	Х	Х	Х	х	х	х	х			
Clinical Global Impression Scale	Х	Х	Х	Х	Х	Х	Х			
PRAS ASD	Х						Х			
Vineland-3	Х						Х			
Side effects checklist		Х	Х	Х	Х	Х	Х			

Subject Recruitment

All potential subjects for this study will be recruited through the Child and Adolescent Psychiatry Department Neurodevelopmental clinic and by Neuropsychological referral.

Subjects:

Inclusion criteria:

- 1) Boys and girls ages 4-17;
- 2) Current diagnosis of Autism Spectrum Disorder as determined by criteria in DSM-5
- 3) Parents of Children ages 4-17 with a current diagnosis of Autism Spectrum Disorder as determined by criteria in DSM-5

Exclusion criteria:

- 1) Unstable medical illness or clinically significant abnormalities on physical examination;
- 2) History of seizures;
- 3) History of Hematological disorders;
- 4) Myocardial infarction within 6 months;
- 5) Current pregnancy or lactation, or inadequate contraception in girls of childbearing potential;
- 6) Current or recent (past 3 months) DSM-5 substance abuse or dependence;
- 7) Illegal substance use within 2 weeks of study initiation;
- 8) Previous treatment with Glutathione;
- 9) Current treatment with N-acetylcysteine, milk thistle, Vitamin C, Vitamin B, Grape Seed Extract, Amino Acids, or Zinc (known to interfere with Glutathione level)
- 11) Current treatment with Dextromethorphan, D-cycloserine, Amantadine, Memantine, Lamotrigine or Riluzole (known to have glutamatergic properties)
- 12) Asthma (given this is rare, but possible worsening of asthma symptoms due to Glutathione)

Assessments:

Existing Data

Before beginning Glutathione, all subjects will have a psychiatric, medical, and family history evaluation completed as part of their standard clinical care.

New Data Collection

At the screening visit, all subjects will receive a physical examination. For all subjects, at the initial visit, blood work will be obtained for a baseline Glutathione level. Glutathione level will also be obtained at study completion. Total amount of blood to be obtained will be 4 teaspoons. PI will obtain neuropsychological evaluations report if it is available.

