The study will end once 24 subjects have been recruited and have completed the study visits. At this point, the data analysis will then begin.

Potential Risks and Benefits:

The study supplement Glutathione may help to decrease problem behaviors and irritability that can be seen in children with Autism Spectrum Disorder. It is also postulated that the information learned from this study will benefit other individuals and children and adolescents with problem behaviors related to Autism Spectrum Disorder in the future.

Page 11 of 17 IRB19-0017 Version 2; date: 4/11/19 Most supplements can cause side effects, but are typically safe. Side effects are usually reversible when the supplement is stopped. The most common side effects associated with Glutathione include; upset stomach, diarrhea, dizziness, dry mouth or headaches and sometimes, but rarely a skin rash, skin flushing or respiratory distress can be seen. As such, patients with asthma or allergies that have resulted in respiratory distress in the past will not be included in this study to ensure safety.

Safety Assessments:

Safety assessments (sitting blood pressure, heart rate, adverse effects, and concomitant medications) will be documented at each visit. In terms of vital signs, those subjects with abnormal blood pressures will be assessed for symptoms of hypo- or hypertension. Asymptomatic subjects will be evaluated each visit for changes in vital signs. In the case of hypertensive emergencies (BP greater than 210/120), appropriate referral to the emergency room will be made. In the case of hypotension (BP less than 90/60), participants will be evaluated for symptoms of hypotension and if symptomatic, appropriate interventions will be made. Subjects who endorse suicidal thoughts at any time during the study will be removed from the study and appropriate clinical intervention (e.g. hospitalization) will be arranged.

At the initial visit, blood work will be obtained for a baseline Glutathione level and an end point Glutathione level will also be obtained at study completion. Assessment of side effects will be done at each visit. Participants will be advised concerning the risk of allergic reactions to Glutathione: skin rash, skin flushing, drop in blood pressure, irregular heartbeat, and respiratory distress. Although is it extremely rare but participants will be advised to visit an emergency room for symptoms suggestive of anaphylactoid reactions.

Adverse Event Reporting:

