Unanticipated (unexpected) problems/events, those that are not already described as potential risks in the consent form, or not part of an underlying disease, will be reported to the IRB within 10 business days. The same will be done for serious problems/events and, in the opinion of the investigator, are possibly, probably or definitely related to the research procedures. A follow-up report will also be submitted to the IRB with any documentation related to a previously submitted adverse event.

Procedure:

Twenty-four (24) subjects will be recruited to receive oral Glutathione reduced in this open-label trial. All parents of the subjects will be provided with informed consent forms and verbal assent from subjects ≥ 6 years of age will be obtained after an age appropriate version of the informed consent forms are read to them. The Child Psychiatry clinicians/nurses, patients and parents will be aware of the medication name and dosing schedules as indicated. The clinic nurse will obtain vitals at each visit. Glutathione will be the only study medication dispensed to subjects for this study. Subjects will be told to take the first dose of study medication after breakfast each day and the second dose in the evening after dinner. Subjects will be told to monitor and report any side effects experienced to the study staff at each visit or immediately if they wish (via one of the

Page 12 of 17 IRB19-0017 Version 2: date: 4/11/19 multiple telephone numbers for the study physicians and study staff given to them at each visit).

Psychotherapy of any form (including cognitive-behavioral therapy) will be reported to the PI during the study.

Subjects will be evaluated with the Aberrant Behavior Checklist (ABC), Social Responsiveness Scale (SRS) and CGI at screening and at each visit for the remainder of the study. Medication side effects will be evaluated at each study visit. A tablet count will be kept for each dose of medication taken to monitor adherence.

Dosing Regimen for Glutathione

The proposed dose range for Glutathione in this study will be 1000mg-3000mg/day based on the subject's weight. A previous observational study of children with Cystic Fibrosis showed that this population responded well and were able to absorb Glutathione with a daily dose of 65mg/kg (10).

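### A child who endorses suicidal thoughts leaves the study, not only the supplement, so scheduled safety follow-up of that child ends at the event

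*Combined protocol and SAP*

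**What the plan says.** The rule is in Safety Assessments: "Subjects who endorse suicidal thoughts at any time during the study will be removed from the study". The same sentence requires that clinical care, such as admission, be arranged. It is the only event in the document with a removal rule. In the same paragraph, a hypertensive emergency leads to referral and symptomatic hypotension to treatment, and neither ends participation.

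That section also fixes when safety is observed: "Safety assessments (sitting blood pressure, heart rate, adverse effects, and concomitant medications) will be documented at each visit". The visit table agrees, with a row for "Side effects checklist" marked at every numbered visit.

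Adverse Event Reporting adds a later step: "A follow-up report will also be submitted to the IRB with any documentation related to a previously submitted adverse event". For serious events it relies on a judgement whether they, "in the opinion of the investigator, are possibly, probably or definitely related to the research procedures".

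The purpose is stated in Project Goals ("The goal of the proposed study is to evaluate the safety and feasibility of oral Glutathione") and in the third item under Aims ("To test whether oral administration of Glutathione supplement is well tolerated as a medical food in children with ASD").

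**The concern.** Stopping the supplement and leaving the study are different acts. The first protects the child. The second also ends data collection. The rule does both, at the only psychiatric event named in the safety section of a trial whose stated goal is safety.

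The study has one arm, so no control group helps in interpreting such an event. Whether it resolves, persists or recurs after the supplement is stopped is one of the few inputs to a judgement of relatedness. Potential Risks and Benefits states that side effects usually go away on stopping. For this event, the rule ends the scheduled observation that could bear on that statement.

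**Working it through.** The document gives no rate, power or dropout figure for this rule, so there is no planned figure to reproduce. The check is a reading of the text and a count of visits.

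**Step 1. What ends and what remains.**
- Ends: visit-based recording of blood pressure, heart rate, adverse effects and concomitant medications (Safety Assessments), and the scales completed at each visit (New Data Collection).
- Remains: the event itself and everything recorded before it; the clinical care that is arranged; and, if the event was submitted, a follow-up report to the IRB. That report passes on whatever documentation exists and schedules no assessment of the child.
- Not found in the document: an early-termination visit, a post-stop safety contact, or follow-up of an event to resolution. The consent form is not in the file.

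**Step 2. Visit dates.** METHODS describes two-weekly and then four-weekly visits, "with one final visit at the end of the study for a total of 5 visits". The dosing schedule puts Visit 1 at Week 0, Visit 2 at Week 2, Visit 3 at Week 4 and Visit 5 at Week 12. Visit 3 dispenses 28 days of supplement, which places Visit 4 at 4 + 28/7 = Week 8. The post-baseline visits are Weeks 2, 4, 8 and 12, four in all.

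**Step 3. Observation lost per removed child on that schedule.** Weeks lost = 12 − week of removal.

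| Removed at | Visits lost (of 4) | Weeks lost (of 12) |
|---|---|---|
| Week 2 | 3 (Weeks 4, 8, 12) | 12 − 2 = 10 |
| Week 4 | 2 (Weeks 8, 12) | 12 − 4 = 8 |
| Week 8 | 1 (Week 12) | 12 − 8 = 4 |

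**Step 4. The other schedule.** The visit table has Visits 1 to 6, so five post-baseline visits, and conflicts with the five-visit total in METHODS. On the table, removal at Visit 2, 3, 4 or 5 loses 4, 3, 2 or 1 of 5 visits. The table gives no weeks. The conclusion is the same on either schedule.

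**Step 5. Separate point: the glutathione endpoint for any early leaver.** New Data Collection and Safety Assessments give two draws, at the initial visit and at study completion. Data Analysis keeps anyone with at least one follow-up visit in the intention-to-treat set with LOCF. A child who leaves between the two draws has only the baseline value. Applied literally, LOCF makes that child's change baseline − baseline = 0, whatever the supplement did.

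**The case against.** **Removal is protective, and care is arranged.** This is true, and a reader might infer from the rule that the child is abandoned or that the event disappears from the data. The document supports neither inference: care is required, the event stays on record and IRB reporting continues. Stopping the supplement and arranging care already give the protection, however, and neither requires ending safety visits.

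**The lost visits were not built for this event.** This stands in part. None of the scheduled scales (ABC, SRS, CGI-Severity) is named as a suicidality measure. Only the general adverse-effects enquiry would record the event's course, so it would be wrong to count each lost visit as a lost suicidality assessment. The fix therefore has to direct that enquiry at the event.

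**Relatedness is judged before the next visit.** This largely stands for the first report, due within 10 business days (about 14 calendar days). After removal at Week 2 the next visit is 14 days later; after Week 4 or 8 it is 28 days later. Later course would mainly feed the follow-up report, which can contain only what someone has collected. A reader might also infer that continued visits would establish causation. One child's course, confounded by admission or other treatment, cannot do that.

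**Other channels exist.** Families have telephone numbers for study staff, recruitment is partly through the department's own clinic, and all subjects are seen in that department. These contacts are unscheduled, so the point survives, but less information is lost in practice than the count of weeks suggests.

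**It may never happen.** This stands. One might put a probability on it: with an assumed per-child risk p, the chance of at least one case in 24 is 1 − (1 − p)^24, which is 21% at p = 1% and 92% at p = 10%. The document supports no value of p, so the range shows only that the answer follows the assumption. It is no evidence of importance.

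**Conclusion.** The point holds in a limited form. As written, the rule ends scheduled study safety follow-up for a child who endorses suicidal thoughts, and no other section restores it. Per affected child, on the METHODS schedule, 3, 2 or 1 remaining visits are lost after removal at Week 2, 4 or 8. How many children would be affected is unknown and may be zero. The conclusion assumes that removal from the study means what it says and that the consent form, which was not available, adds no follow-up.

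The LOCF point is separate and minor. A reader might infer that the primary result will be biased toward no change. The document does not settle that. Data Analysis also refers to all available data and to random regression, and never says that a baseline value may stand as a post-treatment value. The study-end statement can also be read as requiring 24 completers.

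**What to change.** Replace the rule with wording such as: *The supplement will be stopped and suitable clinical care arranged. With parental consent, and where clinically appropriate, the child continues the remaining scheduled safety visits, with the adverse-effects enquiry asking about the course of the event, at least until it resolves.*

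The change uses visits already planned. It costs an amendment through the IRB and matching consent text. Some families will decline, and visits may be unsuitable during a crisis or admission.

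For any child who stops early, for whatever reason, state that baseline is not carried forward as a zero change. Leave the 12-week glutathione change missing and report how many are missing. If a sample is taken at the stopping visit, list it separately with the dose at that time. If titrated as planned, that is 1000 mg/day up to the Week 2 visit, 2000 mg/day up to Week 4, and 2000 or 3000 mg/day by weight group up to Week 8. Such a sample does not replace the 12-week value, and a draw may be inappropriate in a crisis.

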Although a number of medications have been used to treat comorbidities associated with ASD such as neuroleptic agents, antidepressants, stimulants and anxiolytics, there is limited evidence about direct pharmacologic treatment of ASD alone. However, complementary and alternative medicine has been showing some potential promise in treatment options for this patient population. There have been some placebo-controlled trials of N-acetylcysteine (NAC) in ASD patients directed toward the treatment of irritability, aggression, self-injurious behavior and tantrums (11). Harden et al. (2012), found a significant reduction in irritability symptoms that were measured by the Aberrant Behavior Checklist in a placebo-controlled pilot trial of NAC in children with ASD (4). Another 12-week randomized, double-blind, placebo-controlled trial of oral NAC in children with ASD; found NAC to be safe; however, it was not noted to have a significant impact on core social impairment seen in ASD, but the authors did indicate that larger scaled trials are needed in order to predict a good treatment response (11).

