The following instruments will be completed at each visit throughout the study: 1) Aberrant Behavior Checklist [ABC], a 58-item parent report subjective scale used for assessing problem behavior in subjects with intellectual and developmental disabilities; 2) Social Responsiveness Scale [SRS], a 65-item parent report questionnaire designed to use with children ages 4-17, providing age- and gender-referenced ranges and assessing social deficits pertaining to autism and

Page 9 of 17 IRB19-0017 Version 2; date: 4/11/19 other domains; and 3) the Clinical Global Impression scale [CGI]; 7 point scale to measure symptom severity. Also, readings of patients' heart rates and blood pressures will be obtained; and assessment of side effects will be done at each visit.

Note on ABC and SRS:

The ABC is a standardized scale used for assessing problem behaviors in subjects with developmental and intellectual disabilities. The items are divided into five subscales: 1) Irritability; 2) Lethargy/Social Withdrawal; 3) Stereotypic Behavior; 4) Hyperactivity; and 5) Inappropriate Speech. High scores are indicative of severe behavioral symptoms. The ABC will be used to track the subjects' problem behaviors and difficulties over the course of the study. The severity of the subjects' problem behaviors must be assessed and examined its relationship with a baseline blood level of glutathione. In addition, by using this scale, we can observe the overall effect of oral Glutathione on problem behaviors, especially comparing the end results to the baseline.

The SRS is being used for the same purpose, although it is being used for secondary outcome measures. It is a parent report questionnaire designed for use with children aged 4-17 and provides age- and gender-referenced, as well as raw scores for the following domains: total score (reflecting severity of social deficits pertaining to autism); receptive, expressive, cognitive and motivational aspects of social behavior; and autistic preoccupations. High scores are also indicative of severe behavioral symptoms.

Note on additional measures:

Clinical Global Impression (CGI) (Severity) scale will be used by the clinician to assess overall severity of problem behaviors in Autism Spectrum Disorder subjects at baseline. This will be used as a secondary outcome measure over the course of the study and relates to Aim #1.

Study Population/Sample Size

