24 male and female outpatients aged 4-17 with a primary diagnosis of Autism Spectrum Disorder.

-Note on sample size: The sample size is low due to this being a pilot feasibility study and the primary aim of the study is not to examine the effectiveness of oral glutathione as a treatment but rather examine the functionality of providing oral glutathione on the blood level, the data will likely be used for future studies on treatment or grant applications. There also is no external sponsor, therefore internal funding limits the number of subjects.

Participant Exclusion:

For this study, children under the age of 4 and adults over the age of 17 will be excluded. The rationale for this is that the study population of interest are pediatric subjects in the children and adolescent age ranges.

Data Analysis:

Primary analyses will be intent-to-treat with last observation carried forward. Changes in the blood level of glutathione will be the primary outcome measure. For both primary and secondary measures, random regression analysis will be conducted using the MIXREG program

Demographic and baseline visit characteristics of the Glutathione treatment patients will be documented. Primary and secondary measures will be examined using analysis of variance modeling analyses (SPSS). The difference in the overall level of posttreatment values, the main effect for treatment, will be the test of primary interest. Analyses will be performed on all available data by the use of an intention-to-treat population (last observation carried forward). All patients who return for at least 1 follow-up visit will be included in the intention-to-treat population. Effect sizes will also calculated using the Cohen effect size index d. A d of 0.2 is considered a small effect size, 0.5 is medium, and 0.8 is large. Partial eta squared (η 2), which is the proportion of the effect + error variance that is attributable to the effect, will be calculated. Interpretation of η 2 is that greater than 0.2 is a large effect size, greater than 0.1 is a medium effect size, and greater than 0.05 is a small effect size.

The CGI severity scale will be used to assess clinically significant change after treatment. For someone to have a clinically significant change, her or his final CGI severity score had to be less than the cutoff score, and her or his change from baseline had to be greater than the reliable change index

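### Entry requires no stable period on psychotropic medicines or behavioural therapy, and no analysis rule uses the recorded changes, so co-treatment response is mixed into the secondary ABC, SRS and CGI results

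*Combined protocol and SAP*

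**What the plan says.** The design is a single open-label arm (Procedure): "Twenty-four (24) subjects will be recruited to receive oral Glutathione reduced in this open-label trial".

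**Entry.** Inclusion (Subjects) is by age and diagnosis: "Current diagnosis of Autism Spectrum Disorder as determined by criteria in DSM-5". The exclusion list bars current use of named supplements because they affect glutathione level (item 9) and six named glutamatergic drugs (item 11). Background and Significance acknowledges that "a number of medications have been used to treat comorbidities associated with ASD such as neuroleptic agents, antidepressants, stimulants and anxiolytics", but the list neither excludes those four classes nor asks that they be stable. It does not mention behavioural therapy. The numbering goes from item 9 to item 11.

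**During the study.** Safety Assessments: "Safety assessments (sitting blood pressure, heart rate, adverse effects, and concomitant medications) will be documented at each visit". Procedure: "Psychotherapy of any form (including cognitive-behavioral therapy) will be reported to the PI during the study". Neither section limits changes or says what follows from one.

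**Analysis.** Data Analysis uses every available rating, with the last observation carried forward. It gives no covariate, censoring rule, subgroup or sensitivity analysis for co-treatment. Its definition of clinically significant change on the CGI has no condition on co-treatment.

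**Interpretation.** The Note on ABC and SRS says that with the ABC "we can observe the overall effect of oral Glutathione on problem behaviors, especially comparing the end results to the baseline".

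**The concern.** A child who started a neuroleptic or a behavioural programme shortly before Visit 1 is eligible. A child who starts one at week 4 stays in, and all later ratings count. These treatments can act directly on what the ABC, SRS and CGI measure. No concurrent arm is available to subtract their effect, so the response becomes part of the change from baseline and could make a child a CGI responder.

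The protocol already screens out co-treatments that would disturb the blood level. It has no comparable safeguard for treatments that would disturb the behaviour ratings.

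What is at stake is the behavioural signal. The hypothesis in Project Goals includes reduced problem behaviour and irritability, and the sample-size note expects the data to support later treatment studies or grant applications. A behavioural effect size that contains an unknown share of co-treatment response would be carried into that planning.

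**Working it through.** **1. What there is to reproduce.** Nothing numerical. The sample size has no stated alpha, power, effect size or SD. It rests on pilot status and on money: "There also is no external sponsor, therefore internal funding limits the number of subjects". The documents also give no rate of co-treatment change, no effect of any co-treatment on the ABC, and no SD for it. The core of the point is therefore a reading of the text.

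**2. The text, side by side.**

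| Question | Where | Answer |
|---|---|---|
| Stable psychotropic dose required at entry? | Inclusion and exclusion criteria | No |
| Stable behavioural therapy required at entry? | Same | No |
| Medicine changes during the study | Safety Assessments | Documented at visits |
| Therapy changes during the study | Procedure | Reported to the investigator |
| Rule using these records | Data Analysis | None |
| How behaviour change is read | Note on ABC and SRS | As the supplement's effect |

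**3. Illustration of size, with assumed inputs.** From the documents: n = 24, one arm. Assumed:
- the true glutathione effect on behaviour is zero;
- k of the 24 children have a co-treatment change;
- each of those children gains e, in units of the SD of the change score;
- the test is a one-sample t-test on change, two-sided at 0.05.

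Expected spurious mean shift = (k / 24) × e.

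- k = 3: 3/24 × 0.5 = 0.06 SD; 3/24 × 1.0 = 0.13 SD
- k = 6: 6/24 × 0.5 = 0.13 SD; 6/24 × 1.0 = 0.25 SD
- k = 9: 9/24 × 0.5 = 0.19 SD; 9/24 × 1.0 = 0.38 SD
- k = 12: 12/24 × 0.5 = 0.25 SD; 12/24 × 1.0 = 0.50 SD

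Chance of a significant result by simulation (100,000 runs per cell):

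| Children changing (k) | e = 0.5 | e = 0.8 | e = 1.0 |
|---|---|---|---|
| 0 | 4.9% | 4.9% | 5.0% |
| 3 | 5.7% | 6.4% | 7.2% |
| 6 | 8.3% | 12.9% | 16.8% |
| 9 | 13.1% | 24.6% | 33.7% |
| 12 | 19.9% | 40.5% | 55.9% |

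The k = 0 row differs from 5% only by simulation error.

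**4. Scale.** With n = 24, the change detectable with 80% power is about 0.60 SD by the t-test; the normal approximation gives (1.960 + 0.842) / √24 = 0.57 SD. A shift of 0.06 to 0.25 SD (3 to 6 children) is well below that. It would distort an effect-size estimate more often than it would produce a significant result by itself.

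**5. What the illustration leaves out.** It credits each child with the full benefit after baseline. A treatment begun before Visit 1 may already be partly reflected in the baseline rating, which would reduce the shift. It also takes every change to be beneficial, whereas stopping or reducing a treatment could move scores the other way.

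**The case against.** The strongest reply is that the study disclaims efficacy. The sample-size note says that effectiveness is not the primary aim, the primary outcome is blood glutathione, and the three numbered Aims are plasma level, feasibility and tolerability. This stands, and it confines the point to secondary outcomes. It does not remove the point, because the Note on ABC and SRS still reads end-versus-baseline change as the supplement's effect.

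Second, the dominant limitation is the missing control arm. That is also true. Expectancy in open parent ratings and regression to the mean would survive any stability rule. Co-treatment change is nevertheless a part that a single-arm study can limit at entry and display in analysis.

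Third, item 10 is absent from the numbered exclusions. It may be a numbering slip or lost text. Nothing visible suggests that it was a stability criterion, but it should be checked.

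Three stronger readings are tempting, and the documents support none of them:

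- **That the bias favours glutathione.** A reader might suppose that children enter when behaviour is at its worst and treatment is being stepped up. The criteria set no minimum ABC, irritability or CGI score, and nothing is said about how often treatment is adjusted in the recruiting clinic.
- **That the bias can be put in ABC points.** This would need a rate of change and a co-treatment effect on a named ABC score. The documents give neither.
- **That a behavioural result which disappears once post-change ratings are removed is not due to glutathione.** Ratings before a change reflect shorter exposure. Under Investigational Agent, children above 40 kg reach the last dose step only at week 4, so for a change at or before week 4 the retained ratings precede it. A result could vanish for that reason, or because few data remain. A result that persists would still be uncontrolled.

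**Conclusion.** The point holds for the secondary behavioural outcomes only. As written, the plan lets a response to a recently started or changed co-treatment enter the ABC, SRS and CGI change, and it provides no means of seeing how much. The plasma-level primary outcome and the feasibility and tolerability aims are not affected by this mechanism.

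Neither size nor direction can be established from the documents. Under the assumed inputs, inflation is slight if about 3 of 24 children change treatment and material if a quarter or more do. The larger figures, for 9 or 12 children, show the shape of the relation and are not forecasts. The conclusion about the text assumes that the missing item 10 is not a stability criterion. This is a cheap improvement, not a flaw that undermines the study.

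**What to change.** 1. **Eligibility.** Add one line requiring no start, stop or dose change of a psychotropic medicine, and no new behavioural or psychotherapy programme, for a fixed period before Visit 1. The length is for the investigator to set. Do not restrict care after entry. Check at the same time whether exclusion item 10 is lost text.
2. **Reporting.** From the records already kept, report the number of children with a co-treatment change and when it occurred.
3. **Supportive analysis.** Pre-specify ABC, SRS and CGI change with ratings made after such a change excluded. State how the excluded visits are handled, since the carry-forward rule would otherwise put the pre-change rating in their place. Note that the retained ratings reflect shorter and possibly lower-dose exposure.
4. **Wording.** Describe behavioural change as uncontrolled whichever way that analysis falls, and amend the Note on ABC and SRS to match.

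Cost: one eligibility line, one supportive analysis from data already collected, and a few words of interpretation. Entry of some children is delayed, by a number the documents do not allow one to estimate, and the supportive analysis uses fewer data from an already small sample.
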